3.3.3 Overall Benefit/Risk Conclusion

IM047-023 has been designed to closely monitor study participants' safety throughout the duration of the study. A comprehensive safety monitoring plan utilizes frequent assessments to monitor for disease relapse which allows the participants to proceed to open-label treatment. Additionally, at the investigator's discretion, rescue therapy can be initiated or dosing of study medication can be discontinued at any time during the study. A comprehensive monitoring of safety will be conducted by the investigators, Clinical Trial Physicians, and an independent DMC.

Given the mechanism of action of ozanimod, data from the preclinical animal model, the positive results from the Phase 2 (RPC01-202) and Phase 3 (RPC01-3101) UC studies, the Phase 2 CD study (RPC01-2201), and an acceptable safety profile observed across indications, ozanimod has the potential to address an unmet need in the pediatric CD population. IM047-023 has a potential favorable benefit/risk profile for pediatric patients with moderate to severe CD who have inadequate response or intolerance to corticosteroids, immunomodulators, or biologic therapy.

Protocol Amendment No.: 02

Approved v 3.0 930181787 3.0

4 OBJECTIVES AND ENDPOINTS

Table 4-1: Objectives and Endpoints

Objective	Endpoint
Primary – Efficacy	
To evaluate the efficacy of ozanimod once daily in pediatric participants with moderately to severely active CD: clinical remission by PCDAI at Week 64	Proportion of participants who achieve PCDAI < 10 at Week 64
To evaluate endoscopic remission at Week 64 by SES-CD	 Proportion of participants achieving SES-CD ≤ 2 or SES-CD ≤ 4 points with no SES-CD subscore > 1 point at Week 64
Secondary – Efficacy (Key)	
To evaluate the efficacy of ozanimod once daily in pediatric participants with moderately to severely active CD: clinical remission by PCDAI at Week 12	Proportion of participants who achieve PCDAI < 10 at Week 12
Secondary – Efficacy (Other)	
To evaluate endoscopic response by SES-CD	• Proportion of participants who achieve SES-CD decrease from Baseline of ≥ 50% (ER-50) at Week 64; Week 12
To evaluate clinical response by PCDAI	 Proportion of participants who achieve reduction in PCDAI score ≥ 12.5 and a total PCDAI score of < 30 points at Week 64; Week 12
To evaluate symptomatic remission (adolescents only)	 Proportion of adolescents who achieve an average daily abdominal pain score ≤ 1 point and an average daily stool frequency ≤ 3 points with abdominal pain and stool frequency no worse than Baseline at Week 64; Week 12
To evaluate change in CD symptoms over time	Change from Baseline in stool frequency score over time Change from Baseline in abdominal pain over time
To evaluate clinical remission by CDAI (adolescents only)	Proportion of adolescents who achieve CDAI score < 150 at Week 64; Week 12
To evaluate clinical response by CDAI (adolescents only)	Proportion of adolescents who achieve CDAI reduction from Baseline of ≥ 100 points or CDAI score < 150 at Week 64; Week 12
To evaluate corticosteroid-free remission	Proportion of participants who achieve a PCDAI score < 10 at Week 64 while remaining corticosteroid free in the prior 12 weeks
- To evaluate corticosteroid-free relinssion	Proportion of participants who achieve a CDAI score < 150 at Week 64 while remaining corticosteroid free in the prior 12 weeks (adolescents only)

Protocol Amendment No.: 02

Table 4-1: Objectives and Endpoints

Objective	Endpoint
To evaluate endoscopic remission at Week 12	 Proportion of participants achieving SES-CD ≤ 2 or SES-CD ≤ 4 points with no SES-CD subscore > 1 point at Week 12
Secondary –Pharmacokinetics	
To characterize the PK of 2 doses of oral ozanimod and its major active metabolites in pediatric participants with moderately to severely active CD	Steady state systemic exposures of ozanimod and CC112273 at Week 20 and throughout the study
Secondary –Pharmacodynamics	
To evaluate the PD effects of 2 dose levels of ozanimod (eg, effects on ALC) in pediatric participants with moderately to severely active CD	Absolute and percent change from Baseline in ALC at Week 64, Week 12, and throughout the study
Secondary – Safety and Tolerability	
To evaluate the safety and tolerability of 2 dose levels of oral ozanimod once daily in pediatric participants with moderately to severely active CD	Number and proportion of participants experiencing AEs, SAEs, AEs leading to discontinuation from treatment, and AESIs throughout the study

Table 4-1: Objectives and Endpoints

Objective	Endpoint

Endpoint Definitions

Key study definitions are provided below (see Table 4-2).

Table 4-2: Selected Endpoint Definitions

Endpoint	Definition	
Clinical remission	CDAI < 150	
Chinical remission	PCDAI < 10 points	
Clinical response	CDAI reduction from Baseline of ≥ 100 points or CDAI score < 150	
	PCDAI reduction from Baseline of ≥ 12.5 and a total PCDAI score of < 30 points	
Endoscopic remission	SES-CD \leq 2 or SES-CD \leq 4 points and with no SES-CD subscore $>$ 1 point	
Endoscopic response	≥ 50% improvement from Baseline in the SES-CD	
Corticosteroid-free remission	PCDAI score < 10 at Week 64 while remaining corticosteroid free in the prior 12 weeks	
	CDAI < 150 at Week 64 and receiving no corticosteroids for CD in the prior 12 weeks	
Histologic remission		
Loss of response		
Symptomatic remission (adolescents only)	Average daily abdominal pain score ≤ 1 point and average daily stool frequency ≤ 3 points with abdominal pain and stool frequency no worse than Baseline	
Abbreviations: CDAI, Crohn's Disease Activity Index;	Activity Index; PCDAI, Pediate SES-CD, Simple Endoscopic Score for Crohn	

Disease.

[figure not shown]
Protocol Amendment No.: 02

5 STUDY DESIGN

5.1 Overall Design

[figure not shown]
This is a Phase 2/3, randomized, double-blind study designed to evaluate the efficacy, safety, and tolerability of oral ozanimod once daily in pediatric participants aged 2 to 17 years inclusive, with moderately to severely active CD (defined as a Pediatric Crohn's Disease Activity Index [PCDAI] score of \geq 30 and an SES-CD score of \geq 6 [or SES-CD \geq 4 in participants with isolated ileal disease] with an inadequate response, intolerance, or loss of response to prior therapy for CD. The study will also evaluate the PK and PD of oral ozanimod administered once daily at 2 dose levels (0.46 or 0.92 mg/day adult equivalent doses) in pediatric participants during a 64-week Induction and Maintenance treatment period.

The co-primary endpoints of the study are the proportion of participants in clinical remission (PCDAI < 10) at Week 64 and the proportion of participants in endoscopic remission (SES-CD \leq 2 or SES-CD \leq 4 points with no SES-CD subscore > 1 point) at Week 64. Key secondary endpoints are provided in Section 4.

Protocol Amendment No.: 02

steady state PK data will be evaluated to adjust the escalation regimen as required.

The treatment that each participant will receive will not be disclosed to the investigator, site staff, participant, Sponsor, or the clinical staff at the contract research organization (CRO) involved with study conduct or data collection/analysis. Access to treatment assignments will be strictly limited to groups directly involved with drug distribution, preparation of unblinded output for the Clinical Science, safety personnel unblinded to treatment for SAE cases, and personnel involved in the conduct of PK assays.

The blind should be maintained for persons responsible for the ongoing conduct of the study through the completion of the Long-term Extension (LTE) Period. Blinded persons may include but are not limited to the Clinical Trial Physician, Clinical Scientist, Clinical Trial Manager, Study Statistician, Data Manager, Programmers and Clinical Research Associates.

[figure not shown]
Protocol Amendment No.: 02

The study will be conducted in compliance with the International Council on Harmonisation (ICH) of Technical Requirements for Registration of Pharmaceuticals for Human Use/Good Clinical Practice (GCP) and applicable regulatory requirements.

will initiate with randomization (1:1) to either a 0.46 mg/day or 0.92 mg/day dose of oral ozanimod.

(ie, 0.46 and 0.92 mg/day)

Participants with concomitant corticosteroid use from Baseline who have initiated a corticosteroid taper are permitted to increase their dose of corticosteroids back to Baseline dose level (see Section 7.7). Participants who initiate therapy with corticosteroids or increase above Baseline dose level during the double-blind period are considered a treatment failure and must be discontinued from the current period but are eligible to proceed to the LTE Period.

At any time, the decision to discontinue participation in the study is left to the discretion of the participant, the participant's parent or legal guardian, or investigator.

Long-term Extension (LTE) Period

Participants will be entering the LTE Period from the Induction or Maintenance Period of this study. Participants eligible for the LTE Period will have either met early discontinuation criteria (see Section 8), completed Week 12 and are non-responders, or have completed Week 64.

The dose at which a participant enters the LTE will be determined by their clinical response at the time of entry into the LTE Period. Participants who have completed Week 64 and are in clinical remission when entering the LTE will receive ozanimod at the same dose as administered in the Induction and Maintenance Periods. Participants who are not in clinical remission at the time of entering the LTE will receive ozanimod at the of 0.92 mg/day adult equivalent dose. In general, the last visit of the Induction/Maintenance Period or the early termination (ET) visit will serve as the first visit of this LTE Period.

Participants who were not in clinical remission when entering the LTE Period and who meet LTE discontinuation criteria described above after at least 7 weeks of treatment (5 weeks in LTE Period and a confirmation visit at least 2 weeks later) in the LTE Period will be discontinued from the study.

Participants who completed Week 64 and were in clinical remission when entering the LTE Period, and who meet discontinuation criterion described above after 5 weeks of treatment in the LTE Period (with confirmation at least 2 weeks later), will receive ozanimod at the 0.92 mg/day adult equivalent dose appropriate for their age for an additional 5 weeks. If the participant continues to

Protocol Amendment No.: 02

meet the discontinuation criterion after the 5 additional weeks of treatment (with confirmation at least 2 weeks later [minimum of 14 weeks in LTE Period]), the participant will be discontinued from the study.

Participants can initiate or increase the dose of concomitant medications for the treatment of CD during the LTE Period and concomitant medications are not subject to dose stabilization requirements. The following medications are allowed at a therapeutic dose for CD (dosage regimen can be adjusted to accommodate mg/kg/day dosing as appropriate): oral 5-aminosalicylic acid (5-ASAs) and corticosteroids (prednisone 1.0 mg/kg/day for weights \leq 40 kg, \leq 40 mg/day for weights \geq 40 kg or equivalent, oral budesonide \leq 9 mg per day, oral beclomethasone \leq 5 mg per day).

Participants who require initiation of an immunomodulatory agent, including, but not limited to, 6-MP, AZA, or biologic therapy; or who require > 3 days of treatment with higher doses of systemic corticosteroids (e.g. prednisone > 1.0 mg/kg/day for weights ≤ 40 kg or > 40 mg/day for weights > 40 kg or equivalent) will be discontinued from the study.

Study Duration for Participants

Participants may spend up to 69 weeks in this study (excluding the up Period) prior to entering the LTE Period. This includes up to 5 weeks in the Screening Period, 12 weeks in the Induction Period, and 52 weeks in the Maintenance Period. For participants not entering LTE, a Safety Follow-up Period will be completed for up to a total of 81 weeks in the study.

Participants who meet early discontinuation criteria (after at least 7 weeks of treatment) as described in Section 8, participants who are non-responders at Week 12, and participants who complete the Week 64 visit, will be eligible to enter the optional LTE Period (see Section 8). Participants entering the LTE Period who continue to demonstrate clinical benefit will receive oral ozanimod daily for up to approximately 4.5 years from their first dose (Day 1), or upon ozanimod approval for pediatric CD participants in their country, or as per local or regional requirements. For participants who enter the optional LTE Period, a Safety Follow-up Period will be completed and the entire participation period of the study may be up to approximately 6 years from the participant's first dose (Day 1).

Participant Input in Study Design

Parents of, and children living with Crohn's Disease are uniquely positioned to help in the drug development process, and their voices have been incorporated into this protocol.

Parents/guardians/participants believe clinical trials are valuable and advance the science and management of CD. They trust their healthcare providers to discuss and recommend clinical trials available within the IBD community.

5.1.1 Data Monitoring Committee and Other Committees

An external, independent DMC will be charged with monitoring accumulating data from the study, as well as general aspects of study conduct.

The committee will meet periodically during the study to review aggregate analyses by treatment group concerning enrollment, treatment compliance, adherence to follow-up schedule, and safety and efficacy data from the study. The DMC will make dose selection and dose adjustment decisions based on the recommendations. The DMC may recommend modifying the study or stopping the study early due to safety concerns based on data reviews.

To assure that all personnel involved in the conduct of the study remain blinded to the results of interim reviews, a blinding plan will be specified in the DMC Charter.

A DMC charter will describe the procedures related to the committee operations in greater detail.

5.2 Number of Participants

Approximately pediatric participants aged 2 to 17 years, inclusive, with moderately to severely active CD with an inadequate response, intolerance, or loss of response to prior therapy for CD will be enrolled in this study.

5.3 End of Study Definition

The start of the trial is defined as the first participant first visit.

End of trial is defined as the last participant last visit *or* the date of receipt of the last data point from the last participant that is required for primary, secondary, and/or exploratory analysis, as pre-specified in the protocol, whichever is the later date.

Study completion is defined as the final date on which data for the primary endpoint were or are expected to be collected, if this is not the same.

[figure not shown]
Participants who continue to demonstrate clinical benefit will be eligible to receive Sponsor-supplied study treatment for a maximum treatment duration as specified per local or regional requirements (see Section 7).

The Sponsor reserves the right to terminate access to Sponsor-supplied study treatment if any of the following occur: a) the study is terminated due to safety concerns; b) the development of ozanimod is terminated for any reason, including but not limited to, lack of efficacy and/or not

[figure not shown]
Protocol Amendment No.: 02

meeting study objectives; c) the participant can obtain ozanimod from a government-sponsored or private health program. In all cases, the Sponsor will follow local requirements.

[figure not shown]
A participant is considered to have completed the study if he/she has completed the last visit or the last procedure shown in Section 2.

Protocol Amendment No.: 02

Protocol Amendment No.: 02

6 STUDY POPULATION

Prospective approval of protocol deviations to recruitment and enrollment criteria, also known as protocol waivers or exemptions, is not permitted.

Protocol Amendment No.: 02

6.1 Inclusion Criteria

Participants are eligible to be included in the study only if all of the following criteria apply:

1) Signed Written Informed Consent

Participants and their parent or guardian must have signed and dated an Institutional Review Board (IRB)/Independent Ethics Committee (IEC)-approved written informed consent form (ICF) and assent in accordance with regulatory, local, and institutional guidelines. This must be obtained before the performance of any protocol-related procedures that are not part of normal patient care.

2) Type of Participant and Target Disease Characteristics

- a) Participant is willing and able to adhere to the study visit schedule and other protocol requirements including is willing and able to swallow a of ozanimod is available.
- b) Participant has been diagnosed with CD ≥ 3 months prior to the Screening Visit. The diagnosis should be confirmed by clinical and endoscopic evidence and corroborated by a histopathology report (Note: Local histopathology sample collection and analysis may also be performed during endoscopy at Screening if no prior report is readily available).
- c) Participant has met each of the following 2 criteria:
 - i) A PCDAI score \geq 30.
 - ii) Participant has a SES-CD score ≥ 6 (or SES-CD ≥ 4 in participants with isolated ileal disease).
- d) Participant has an inadequate response, intolerance, or loss of response to at least 1 of the following treatments for CD (see Appendix 5).
 - corticosteroids (eg, oral prednisone, oral budesonide MMX, intravenous [IV] corticosteroids).
 - ii) immunomodulators (eg, AZA, 6-MP, cyclosporine, MTX).
 - iii) biologic therapy (eg, ustekinumab, abatacept, infliximab, etanercept, adalimumab, anakinra, rituximab, vedolizumab).
 - iv) other systemic immunomodulatory therapies for CD.
- e) If the participant is taking the following background therapies for CD, a stable dose must be maintained as indicated below (dosage regimen can be adjusted to accommodate mg/kg/day dosing as appropriate):
 - i) Oral aminosalicylates (eg, mesalamine, sulfasalazine, olsalazine, balsalazide), the dose must have been stable starting 3 weeks prior to Screening endoscopy.
 - ii) Prednisone (≤ 0.5 mg/kg/day up to 20 mg/day), the dose must have been stable starting 2 weeks prior to Screening endoscopy and must remain stable through the first 5 weeks of treatment.
 - iii) Oral budesonide therapy (doses \leq 9 mg per day) or oral beclomethasone (doses \leq 5 mg per day), the dose must have been stable starting 2 weeks prior to Screening endoscopy and must remain stable through the first 5 weeks of treatment.
- a) Participant must have documentation of vaccinations per standard immunization schedule including complete varicella vaccination at least 30 days prior to randomization (Day or

3) Age of Participant

a) Participant must be age 2 to 17 years, inclusive at the time of informed consent/assent.

Note: Participants with a weight below the 5th percentile for age (per CDC growth charts)²¹ should be discussed with the Clinical Trial Physician or designee prior to enrollment.

4) Reproductive Status

For the purposes of this study, female of childbearing potential (FOCBP) is defined as a female participant ≥ 12 years of age or has reached menarche, and 1) has not undergone a hysterectomy (the surgical removal of the uterus) or bilateral oophorectomy (the surgical removal of both ovaries) or 2) has not been postmenopausal for at least 24 consecutive months (that is, has had menses at any time during the preceding 24 consecutive months).

Investigators shall counsel FOCBP participants on the importance of pregnancy prevention and the implications of an unexpected pregnancy.

- The investigator shall evaluate the effectiveness of the contraceptive method in relationship to the first dose of study intervention.
- Local laws and regulations may require the use of alternative and/or additional contraception methods.

a) Female Participants:

- i) Females who are not of childbearing potential are exempt from contraceptive requirements.
 - (1) If at any time during the study the ability to become pregnant changes, they will no longer be exempt from contraceptive requirements. The investigator will educate the participant regarding abstinence or contraception options and the correct and consistent use of effective contraceptive methods in order to successfully prevent pregnancy.
- ii) FOCBP must have a negative highly sensitive serum pregnancy test (minimum sensitivity 25 IU/L or equivalent units of human chorionic gonadotropin) prior to randomization.
- Additional requirements for pregnancy testing during and after study intervention are located in Section 2.
- The investigator is responsible for review of medical history, menstrual history, and recent sexual activity to decrease the risk for inclusion of a woman with an early undetected pregnancy. At each visit, the investigator will ask the participant if menarche has occurred since the last visit and this information will be recorded in the electronic case report form (eCRF).
 - iii) FOCBP must agree to follow instructions for method(s) of contraception defined in Appendix 4 and as described below and included in the ICF.
 - iv) FOCBP are permitted to use hormonal contraception methods (as described in Appendix 4).

Protocol Amendment No.: 02

Clinical Protocol BMS-986374

- v) A female participant is eligible to participate if she is not pregnant or breastfeeding, and at least 1 of the following conditions applies:
 - (1) Is not a FOCBP OR
 - (2) Is a FOCBP and using a contraceptive method that is highly effective (with a failure rate of < 1% per year), with low user dependency, as described in Appendix 4 during the intervention period and for at least 90 days after and agrees not to donate eggs (ova, oocytes) for the purpose of reproduction for the same time period

[figure not shown]

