APPENDIX 4 WOMEN OF CHILDBEARING POTENTIAL DEFINITIONS AND METHODS OF CONTRACEPTION

Appendix 4 provides general information and definitions related to Woman of Childbearing Potential and methods of contraception that can be applied to most clinical trials. For information specific to this study regarding acceptable contraception requirements for female and male participants, refer to the Methods of Contraception table in this appendix. Only the contraception methods that are highly effective (with a failure rate of < 1% per year), with low user dependency, are acceptable for this study.

DEFINITIONS

Woman of Childbearing Potential (WOCBP)

A woman is considered fertile following menarche and until becoming postmenopausal unless permanently sterile. Permanent sterilization methods include hysterectomy, bilateral salpingectomy, and bilateral oophorectomy.

Women in the following categories are not considered WOCBP:

- Premenarchal
- Premenopausal female with 1 of the following:
 - Documented hysterectomy
 - Documented bilateral salpingectomy
 - Documented bilateral oophorectomy

Note: Documentation can come from the site personnel's review of the participant's medical records, medical examination, or medical history interview.

- Postmenopausal female
 - A postmenopausal state is defined as 12 months of amenorrhea in a woman over age 45 years in the absence of other biological or physiological causes. In addition, females under the age of 55 years must have a serum follicle-stimulating hormone (FSH) level > 40 mIU/mL to confirm menopause.

Note: Females treated with hormone replacement therapy (HRT) are likely to have artificially suppressed FSH levels and may require a washout period in order to obtain a physiologic FSH level. The duration of the washout period is a function of the type of HRT used. Suggested guidelines for the duration of the washout periods for HRT types are presented below. Investigators should use their judgement in checking serum FSH levels.

- 1-week minimum for vaginal hormonal products (rings, creams, gels)
- 4-week minimum for transdermal products
- 8-week minimum for oral products

Protocol Amendment No.: 02

Clinical Protocol BMS-986374 IM047023 Ozanimod

Other parenteral products may require washout periods as long as 6 months. If the serum FSH level is > 40 mIU/mL at any time during the washout period, the woman can be considered postmenopausal.

End of Relevant Systemic Exposure

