End of relevant systemic exposure is the timepoint where the Investigational Medicinal Product (IMP) or any active major metabolites have decreased to a concentration that is no longer considered to be relevant for human teratogenicity or fetotoxicity. This should be evaluated in context of safety margins from the no-observed-adverse-effect level or the time required for 5 half-lives of the IMP to pass.

METHODS OF CONTRACEPTION

Local laws and regulations may require use of alternative and/or additional contraception methods.

Highly Effective Contraceptive Methods That Are User Dependent

Failure rate of < 1% per year when used consistently and correctly.^a

- Combined (estrogen- and progestogen-containing) hormonal contraception associated with inhibition of ovulation and/or implantation. (This method of contraception can only be used by WOCBP participants in studies where hormonal contraception is permitted by the study protocol.)^b
 - Oral (birth control pills)
 - Intravaginal (rings)
 - Transdermal
- Combined (estrogen-and progestogen-containing) hormonal contraception must begin at least 30 days prior to initiation of study therapy.
- Progestogen-only hormonal contraception associated with inhibition of ovulation. (This
 method of contraception can only be used by WOCBP participants in studies where
 hormonal contraception is permitted by the study protocol.)^b
 - Oral
 - Injectable
- Progestogen-only hormonal contraception must begin at least 30 days prior to initiation of study therapy.

Highly Effective Methods That Are User Independent

- Implantable progestogen-only hormonal contraception associated with inhibition of ovulation and/or implantation. (This method of contraception can only be used by WOCBP participants in studies where hormonal contraception is permitted by the study protocol.)^b
- Intrauterine device.

Protocol Amendment No.: 02

- Intrauterine hormone-releasing system (IUS). (This method of contraception can only be used by WOCBP participants in studies where hormonal contraception is permitted by the study protocol.)^{b,c}
- Bilateral tubal occlusion.

Vasectomized partner

Having a vasectomized partner is a highly effective contraception method provided that the partner is the sole male sexual partner of the WOCBP and the absence of sperm has been confirmed. If not, an additional highly effective method of contraception should be used.

Sexual abstinence.

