Sexual abstinence is considered a highly effective method only if defined as refraining from heterosexual intercourse during the entire period of risk associated with the study treatment. The reliability of sexual abstinence needs to be evaluated in relation to the duration of the study and the preferred and usual lifestyle of the participant.

- Continuous abstinence must begin at least 30 days prior to initiation of study therapy.
- It is not necessary to use any other method of contraception when complete abstinence is elected.
- WOCBP participants who choose complete abstinence must continue to have pregnancy tests, as specified in Section 2.
- Acceptable alternate methods of highly effective contraception must be discussed in the event that the WOCBP participant chooses to forego complete abstinence.
- Periodic abstinence (including, but not limited to, calendar, symptothermal, postovulation methods), withdrawal (coitus interruptus), spermicides only, and lactational amenorrhea method (LAM) are not acceptable methods of contraception for this study.

NOTES:

- Typical use failure rates may differ from failure rates when contraceptive methods are used consistently and correctly. Use should be consistent with local regulations regarding the use of contraceptive methods for participants in clinical studies.
- b Hormonal contraception may be susceptible to interaction with the study treatment, which may reduce the efficacy of the contraceptive method. Hormonal contraception is permissible only when there is sufficient evidence that the IMP and other study medications will not alter hormonal exposures such that contraception would be ineffective or result in increased exposures that could be potentially hazardous. In this case, alternative methods of contraception should be utilized. For information specific to this study regarding permissibility of hormonal contraception, refer to .Sections 6.1 INCLUSION CRITERIA and 7.7.1 PROHIBITED AND/OR RESTRICTED TREATMENTS of the protocol.
- IUSs are acceptable methods of contraception in the absence of definitive drug interaction studies when hormone exposures from intrauterine devices do not alter contraception effectiveness. For information specific to this study regarding permissibility of hormonal contraception, refer to .Sections 6.1 INCLUSION CRITERIA and 7.7.1 PROHIBITED AND/OR RESTRICTED TREATMENTS of the protocol.

Protocol Amendment No.: 02

Clinical Protocol BMS-986374

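### Section 6.1 and Appendix 4 leave it unclear whether user-dependent hormonal contraception is accepted, and they classify premenarchal girls aged 12 or over in opposite ways

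*Combined protocol and SAP*

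**What the plan says.** Section 6.1, criterion 4 (Reproductive Status), contains these provisions:

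- Item a)iii makes Appendix 4 binding: "FOCBP must agree to follow instructions for method(s) of contraception defined in Appendix 4".
- Item a)iv gives a permission: "FOCBP are permitted to use hormonal contraception methods (as described in Appendix 4").
- Item a)v)(2) sets the eligibility standard for a participant of childbearing potential: "using a contraceptive method that is highly effective (with a failure rate of < 1% per year), with low user dependency". It applies during treatment and for at least 90 days afterwards.
- The term FOCBP, introduced as the definition for this study, "is defined as a female participant ≥ 12 years of age or has reached menarche", subject to surgical and menopausal exemptions.

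Appendix 4 describes its content as general information on "methods of contraception that can be applied to most clinical trials". The same paragraph sends the reader to the appendix's own methods table for requirements specific to this study, and says that only highly effective methods with low user dependency are acceptable here.

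The table has a heading for highly effective user-dependent methods. It covers combined oral, vaginal-ring and transdermal products and progestogen-only oral and injectable products. Each entry may be used where the protocol permits hormonal contraception, and each carries a start rule, for example: "Combined (estrogen-and progestogen-containing) hormonal contraception must begin at least 30 days prior to initiation of study therapy".

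On the definition, Appendix 4 uses the term WOCBP. Under "Women in the following categories are not considered WOCBP", the first entry is premenarchal females.

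Notes b and c of the table refer the reader, for study-specific permissibility of hormonal contraception, to Section 6.1 and to "7.7.1 PROHIBITED AND/OR RESTRICTED TREATMENTS of the protocol".

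**The concern.** Table 3.3.1-1 names embryofetal toxicity as a risk, on nonclinical evidence of teratogenicity. Its mitigation is highly effective contraception and regular pregnancy testing in FOCBP. That mitigation works only if every site can tell from the protocol who is covered and which methods count.

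The text does not settle either question cleanly. A site that works from item iv and the methods table sees pills listed, finds the stated condition for their use met, and has a start rule to apply. A site that works from item v)(2) sees a standard that those methods do not meet. On coverage, a premenarchal 12-year-old is inside the definition in one section and outside it in the other. If sites read different pages, they could treat the same adolescent differently at enrolment. A participant on a method that v)(2) does not accept could then be dosed without the deviation being recognised.

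**Working it through.** No arithmetic applies. The check sets the passages side by side and runs typical participants through them.

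**Method rule**

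| Participant's method | 6.1 item iv | Appendix 4 table | 6.1 item v)(2) and Appendix 4 opening |
|---|---|---|---|
| Combined pill, started at least 30 days before study therapy | Permitted (hormonal) | Listed as highly effective, user dependent; condition and start rule met | Not met: not low user dependency |
| Progestogen implant or hormone-releasing intrauterine system | Permitted (hormonal) | Listed as user independent | Met |
| Condom | Not relevant | Listed as less than highly effective | Not met |

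1. The restrictive rule appears twice in matching terms, in v)(2) and in the Appendix 4 opening.
2. The permissive route has three links. Item iv permits hormonal methods. The table makes its user-dependent hormonal entries conditional on just such a permission. The Appendix 4 opening names that table as the place to look for this study's requirements.
3. Nothing under the user-dependent heading says that its methods fall outside this study's rule. Yet the table does make study-specific exclusions elsewhere: it says that periodic abstinence, withdrawal, spermicide alone and lactational amenorrhea are not acceptable for this study.
4. The pill row is therefore where the text gives two answers. The implant row shows that items iv and v)(2) can both be satisfied.

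**Definition of childbearing potential**

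| Participant (no surgical exemption) | Section 6.1 (FOCBP) | Appendix 4 (WOCBP) |
|---|---|---|
| Under 12, premenarchal | No | No |
| Any age, past menarche | Yes | Yes |
| 12 or over, premenarchal | Yes | No |

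5. Only the last row differs. The classification decides whether she enters under v)(1) or must meet v)(2), and whether the serum pregnancy test that Section 6.1 requires of FOCBP before randomization applies to her.
6. The definitions differ in two further ways. Section 6.1 uses 24 months for menopause and Appendix 4 uses 12 months over age 45, which has no practical effect at ages 2 to 17. Appendix 4 also exempts bilateral salpingectomy, which Section 6.1 does not list.

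**Cross-reference**

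7. Section 7.7.1 is Steroid Taper. The title cited in notes b and c belongs to Section 7.7.2, which does not mention hormonal contraception. A reader who finds the right section still gets no answer on user-dependent methods.

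**The case against.** The strongest reply is that there is one rule and it is stated twice. Appendix 4 itself limits this study to low-user-dependency methods and calls its content general. Section 6.1 requires all inclusion criteria to be met, so item iv alone confers nothing: it says only that hormonal methods are not barred as a class, and v)(2) then narrows the choice. The implant and the hormonal intrauterine system satisfy both. On the definition, Section 6.1 is worded as the one for this study, Appendix 4 defines a differently named term, and item iii sends sites to the appendix for methods rather than for the definition. Menarche is also asked about and recorded at each visit.

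Much of this stands. A reader might infer that Section 6.1 and Appendix 4 set opposing method rules. They do not, because both state the restriction. A reader might also infer that pills are accepted because the list of unacceptable methods omits them. That argument fails, since condoms are omitted too and are plainly excluded by v)(2). The 7.7.1 reference, taken alone, is a clerical slip.

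The reply does not remove the ambiguity. The appendix calls itself general, but it also names its table as the study-specific source, and the user-dependent heading in that table is left unmarked. The wording of Section 6.1 suggests that its definition prevails, but no passage says so.

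**Conclusion.** The point holds as an unresolved inconsistency in eligibility and safety text. Read strictly, with all criteria applied together, a participant on a pill fails v)(2). But item iv and the unmarked, study-specific table give a site reasonable grounds to accept her. The two definitions classify a premenarchal girl aged 12 or over in opposite ways, without a stated order of precedence.

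The size is limited. A reader might infer that every girl aged 12 to 17 is affected. The documents do not support that: the method question arises for girls using user-dependent methods, and the definition question for premenarchal girls aged 12 or over. Girls past menarche who use a user-independent method, or complete abstinence (which the table lists under its user-independent heading), get the same answer on every page. The number affected cannot be derived. Section 3.2's figure that 80% of paediatric inflammatory bowel disease cases are aged 10 to 18 describes neither this trial's girls nor their contraceptive use.

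Endpoints and analyses are not touched. The conclusion assumes that text not available here does not already settle the matter, in particular the consent form, which item iii says also carries the contraception instructions, and the cells of the schedule of events. Whether sites would in practice test or enrol differently cannot be judged from the documents.

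**What to change.** Reconcile the passages by amendment:

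- Use one definition of childbearing potential in Section 6.1 and Appendix 4, under one term.
- Mark each heading of the Appendix 4 methods table as acceptable or not acceptable in this study, in agreement with criteria 4)a)iv and v)(2).
- Correct the reference in notes b and c from 7.7.1 to 7.7.2.

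The sponsor decides which definition and which methods apply; this review takes no position on either.

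The cost is amendment wording, matching consent text, and a re-check of the method used by some current participants. Design, endpoints and sample size are unaffected.
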